## 5.8. Toxicity Management Guidelines

Dose modifications should occur based on the emerging safety profile of Debio 1562 and the known safety risks of rituximab.

Frequent AEs observed in patients receiving single agent Debio 1562 included Grade 3/4 neutropenia, febrile neutropenia, thrombocytopenia, fever and infusion reaction. The complete safety risk profile of Debio 1562 is detailed in the Debio 1562 IB.

For details on the most commonly-reported toxicities associated with rituximab please refer to the rituximab label.

**Table 5** should be used as a guide to help investigators assess study treatment related toxicities. Potential overlapping toxicities include fever, infusion-related reaction, and delayed-onset neutropenia. Investigators should reduce or discontinue Debio 1562 for Grade 3-4 non-hematologic toxicities based on clinical judgment, and should manage rituximab induced toxicity per label ([Section 5.9](#)).

**Table 5: Debio 1562 and Rituximab Toxicities**

AE	Debio 1562 ( $\geq 10\%$ of patients in monotherapy)	Rituximab (per label)
Fever	•	•
Infusion related reaction	•	•
Neutropenia	•	
Delayed onset Neutropenia		•
Anemia	•	
Asthenia	•	
AST/ALT increase	•	
Decreased appetite	•	
Diarrhea	•	
Dyspnoea	•	
Fatigue	•	
Febrile neutropenia	•	
Hypokalaemia	•	
Muscle weakness	•	
Nausea	•	
Oedema – peripheral	•	
Thrombocytopenia	•	
Bowel obstruction and perforation		•
Cardiac arrhythmias		•

AE	Debio 1562 (≥ 10% of patients in monotherapy)	Rituximab (per label)
Chills		•
Infection		•
Interstitial pneumonitis		•
Lymphopenia		•
Mucocutaneous reactions		•
Progressive multifocal leukoencephalopathy		•
Reactivation of hepatitis B		•
Renal toxicity		•
Severe infusion related reaction		•
Tumor Lysis Syndrome		•

### 5.8.1. Monitoring and Management of Tumor Lysis Syndrome (TLS)

Acute renal failure, hyperkalemia, hypocalcemia, hyperuricemia, or hyperphosphatemia from tumor lysis, can occur within 12 - 24 hours after the first infusion with rituximab and may be fatal. Signs of TLS have also been observed in patients receiving Debio 1562. Patients with high tumor burden and/or high circulating lymphocyte counts ( $> 25 \times 10^9/L$ ) are at greater risk for TLS and should be adequately hydrated beginning 12 - 24 hours prior to the infusion of Debio 1562 (e.g. 2 L within 12 - 24 hours prior to infusion – roughly 170 cc every two hours).

Any patient experiencing TLS or at risk for TLS should be managed according to institutional practice.

### 5.8.2. Monitoring and Management of Cytopenias

Cytopenias (neutropenia and thrombocytopenia) have been observed in patients treated with rituximab as well as Debio 1562. In patients receiving rituximab monotherapy at  $375 \text{ mg/m}^2$  IV weekly for relapsed or refractory low-grade or follicular NHL, Grade 3-4 neutropenia occurred in 6% and grade 3-4 thrombocytopenia occurred in 2% ([Rituxan® \(rituximab\) Package Insert 2014](#)). In NHL patients who received Debio 1562 monotherapy at the dose of 0.7 mg/kg, Grade 3 neutropenia was the highest grade reported.

Patients experiencing severe cytopenia should follow the recommendations of dose-modification and additional corrective/preventive measures (such as granulocyte colony-stimulating factor [G-CSF]) present in this protocol ([Section 5.9](#)). The type of G-CSF support will be determined by the study physician, as well as the clinical judgement to decide the duration of such treatment.

If a patient develops Grade 4 thrombocytopenia lasting  $>7$  days, study treatment should be terminated and the toxicity should be followed until resolution or stabilization ([Section 5.9.2](#)).

### **5.8.3. Monitoring and Management of Rituximab-associated Bowel Obstruction and Bowel Perforation**

Patients receiving rituximab should be continually monitored for signs or symptoms of bowel obstruction and bowel perforation. Perforations have been shown to occur at higher frequency in patients who have received radiation therapy. Signs and symptoms of bowel obstruction include intermittent abdominal pain, nausea, vomiting, diarrhea, constipation, and abdominal distension. Signs and symptoms of bowel perforation include fever, nausea, vomiting, hematemesis, chills, and severe stomach pain. Patients are advised to notify their treating physician immediately if they experience any of the signs or symptoms described above. If a positive diagnosis of gastrointestinal perforation is made, rituximab should be immediately discontinued and the patient should be treated as per institutional guidelines.

### **5.8.4. Monitoring and Management of Rituximab-induced Progressive Multifocal Leukoencephalopathy (PML)**

John Cunningham virus infection resulting in PML and death can occur in patients receiving rituximab and it has been shown to occur more frequently in patients who received rituximab in combination with chemotherapy or as part of a hematopoietic stem cell transplant. Most cases of PML were diagnosed within 12 months of their last infusion of rituximab. Consider the diagnosis of PML in any patient presenting with new-onset neurologic manifestations. Evaluation of PML includes, but is not limited to, consultation with a neurologist, brain magnetic resonance imaging (MRI), and lumbar puncture. If a positive diagnosis of PML is made, rituximab should be discontinued.

### **5.8.5. Monitoring and Management of Rituximab-induced Renal Toxicity**

Severe, including fatal, renal toxicity has been shown to occur after rituximab administration in patients with NHL. Renal toxicity has occurred in patients who experience TLS. Patients should be monitored closely for signs of renal failure, including but not limited to weakness, shortness of breath, confusion, metallic taste in mouth, fluid retention, nausea, flank pain, seizures, and decreased urine output. Rituximab should be discontinued in patients experiencing rising serum creatinine or oliguria. Patients experiencing renal failure should be managed according to institutional guidelines.

### **5.8.6. Monitoring of Rituximab-induced Cardiovascular Toxicity**

Cardiac toxicity has been reported in patients receiving rituximab. Cardiac monitoring should be performed during and after all infusions of rituximab for patients who develop clinically significant arrhythmias. Rituximab should be discontinued in patients experiencing serious or life-threatening cardiac arrhythmias. Patients experiencing cardiac toxicity should be managed according to institutional guidelines.

### **5.8.7. Monitoring of Rituximab-induced Serious Infections**

Serious, sometimes fatal bacterial, fungal, or viral (new or reactivated) infections have been shown to occur in patients receiving rituximab, during therapy and up to one year following the completion of rituximab-based therapy. Reported new or reactivated viral infections include cytomegalovirus, herpes simplex virus, parvovirus B19, varicella zoster virus, West Nile virus,

and hepatitis B virus (HBV) and hepatitis C virus. Patients should be monitored for signs and symptoms of infections. Rituximab should be discontinued in patients experiencing serious infections; patients should receive anti-infective therapy as per institutional guidelines.

#### **5.8.7.1. Monitoring and Management of Rituximab-induced HBV Reactivation**

HBV reactivation with fulminant hepatitis, hepatic failure, and death has been shown to occur in patients with hematologic malignancies who received rituximab. The median time to diagnosis of hepatitis was approximately four months following the first dose of rituximab and approximately one month after the last dose. Known HBV carriers can participate in this study provided they are HBsAg PCR negative and are receiving antiviral therapy. Rituximab should be discontinued in patients who develop viral hepatitis; patients should receive appropriate treatment including antiviral therapy as per institutional guidelines.

#### **5.8.8. Monitoring of Rituximab-induced Severe Mucocutaneous Reactions**

Mucocutaneous reactions, some with fatal outcome, have been shown to occur in patients treated with rituximab. These reactions include paraneoplastic pemphigus, Stevens-Johnson syndrome, lichenoid dermatitis, vesiculobullous dermatitis, and toxic epidermal necrolysis. The onset of these reactions has varied from 1 to 13 weeks following rituximab exposure. Rituximab should be discontinued in patients experiencing severe mucocutaneous reactions.

### **5.9. Debio 1562 and Rituximab Dose Modifications**

#### **5.9.1. Delay or Skip Dosing of Study Treatment**

In order for a patient to receive any study treatment (Debio 1562 alone or Debio 1562 and rituximab), the following re-treatment criteria must be met.

- ANC must be  $\geq 1.0 \times 10^9/L$  ( $1000/mm^3$ )
- Platelet count must be  $\geq 50 \times 10^9/L$  ( $50,000/mm^3$ )
- All non-hematologic toxicities must be  $\leq$  Grade 2 (except alopecia) or returned to baseline

**Cohort A and B:** If the retreatment criteria are not met on Day 1 of a given cycle, the patient should be re-evaluated within 48-72 hours, and dosing should be delayed until the criteria are met.

If the retreatment criteria are met within 14 days, study treatment should resume at planned or reduced dose (see [Section 5.9.2](#)), and the study physician may opt for the routine administration of secondary prophylaxis with G-CSF during following cycles.

If the retreatment criteria are met within 14-21 days, study treatment should resume at planned or reduced dose (see [Section 5.9.2](#)), and secondary prophylaxis with G-CSF should be administered if the delay was due to unmet hematological parameters.

If dosing is delayed for  $> 21$  days due to unmet retreatment criteria, both study treatments should be discontinued (see [Section 5.9.2](#)).

**Cohort B:** If the retreatment criteria are not met on Day 8 or Day 15 of a given cycle, dosing of Debio 1562 should be skipped on that visit, secondary prophylaxis with G-CSF will be indicated

and the retreatment criteria will be re-evaluated at the next visit when infusion is planned to occur. If the retreatment criteria are not met on Day 1 of the next cycle, the rules described above for the delay on Day 1 of any given cycle will apply.

### 5.9.2. Dose Modifying Events (DME)

Dose Modifying Events (DMEs) are defined as any adverse events that require dose reduction or discontinuation of the study treatment.

#### 5.9.2.1 Adverse Events Requiring Permanent Study Treatment Discontinuation

Both Debio 1562 and rituximab should be permanently discontinued in the case of the following treatment-related events:

- $\geq$  Grade 3 cardiac event
- $\geq$  Grade 3 cutaneous reactions related to rituximab treatment
- Other non-hematologic events of Grade 4 severity
- Grade 4 thrombocytopenia lasting  $>7$  days
- $\geq$  Grade 3 neuropathy
- Dose delay  $> 21$  days due to unmet retreatment criteria

Rituximab should be permanently discontinued in patients experiencing the AEs listed in [Table 6](#).

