**Table 6: Adverse Events Requiring Permanent Discontinuation of Rituximab**

Severity Grade (CTCAE v4.03 Grade)	Adverse Event
Any Grade	Bowel Perforation
Grade $\geq 3$	Cardiac Arrhythmias
Any Grade	Hypersensitivity and/or Allergic Reactions to rituximab
Grade $\geq 3$	Infections
Grade $\geq 3$	Mucocutaneous Reactions
Any Grade	Progressive Multifocal Leukoencephalopathy (PML)
Grade $\geq 3$	Renal Failure
Any Grade	Viral Hepatitis

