#### 5.9.2.2 Adverse Events Requiring Dose Reduction

Rituximab dose reductions are not allowed. If patients do not tolerate treatment with rituximab, they may continue on Debio 1562 alone.

For **Cohort A**, dose reduction of Debio 1562 will occur as follows:

- 0.7 mg/kg → 0.4 mg/kg

For **Cohort B**, dose reduction of Debio 1562 will occur as follows:

- 0.4 mg/kg → 0.2 mg/kg
- 0.2 mg/kg → 0.1 mg/kg

Dose of Debio 1562 should be reduced in patients experiencing the AEs below:

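### The protocol's rituximab stopping rules do not agree on which drug stops for severe skin reactions and arrhythmias, or on the trigger for renal events and, less certainly, infections

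*Protocol*

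**What the plan says.** Section 5.9.2.1 of the protocol opens with a both-drug rule: "Both Debio 1562 and rituximab should be permanently discontinued in the case of the following treatment-related events". The list that follows includes, at the stated grade or higher, "Grade 3 cardiac event" and "Grade 3 cutaneous reactions related to rituximab treatment".

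The same section then points to a separate list, Table 6, titled "Adverse Events Requiring Permanent Discontinuation of Rituximab". Among its eight rows are cardiac arrhythmias, infections, mucocutaneous reactions and renal failure, each from Grade 3 upwards. The table carries no condition about relatedness.

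Section 5.8 gives its own stopping sentences for the same kinds of event:

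- 5.8.5 (renal): "Rituximab should be discontinued in patients experiencing rising serum creatinine or oliguria".
- 5.8.6 (cardiac): "Rituximab should be discontinued in patients experiencing serious or life-threatening cardiac arrhythmias".
- 5.8.7 (infection): "Rituximab should be discontinued in patients experiencing serious infections".
- 5.8.8 (skin): rituximab is stopped for severe mucocutaneous reactions; Debio 1562 is not mentioned.

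Section 5.9.2.2 adds: "If patients do not tolerate treatment with rituximab, they may continue on Debio 1562 alone".

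The opening of Section 5.8 tells investigators to handle rituximab toxicity according to the label and refers them to Section 5.9. It does not rank the two.

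**The concern.** An investigator with a patient who has one of these events can find more than one rule that applies, and the rules do not lead to the same action. For skin reactions and arrhythmias the open question is whether Debio 1562 also stops. For renal events, and perhaps infections, it is whether rituximab stops at all.

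Two things are at stake. The first is patient safety: the renal, infection and mucocutaneous sections all mention fatal outcomes. The second is the analysis. Safety and tolerability is a primary objective. SAP Section 10.3.1 tabulates TEAEs that lead to discontinuation by study treatment, as well as all dose-modifying events. Protocol Section 5.9.2 defines a dose-modifying event by what the protocol requires, namely reduction or discontinuation. If the requirement is unclear, so is the definition of that table.

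**Working it through.** There is no figure in the plan to reproduce and no arithmetic beyond a count of rows. The check sets the rules side by side, event by event.

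| Event | Section 5.8 | Section 5.9.2.1, both-drug list | Table 6, rituximab list |
|---|---|---|---|
| Skin reaction | 5.8.8: severe; rituximab | Grade 3 or higher, rituximab-related; both drugs | Grade 3 or higher; rituximab |
| Arrhythmia | 5.8.6: serious or life-threatening; rituximab | Grade 3 or higher cardiac event, treatment-related; both drugs | Grade 3 or higher; rituximab |
| Renal | 5.8.5: creatinine rise or oliguria, no grade; rituximab | Not named (Grade 4 falls under the general non-hematologic item) | Grade 3 or higher renal failure; rituximab |
| Infection | 5.8.7: serious; rituximab | Not named (same remark) | Grade 3 or higher; rituximab |

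Test cases:

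1. *Grade 3 skin reaction caused by rituximab.* Section 5.9.2.1 stops both drugs. Table 6 and Section 5.8.8 stop rituximab and are silent on Debio 1562, and Section 5.9.2.2 permits Debio 1562 alone. Relatedness does not separate the rules: the both-drug item is expressly about rituximab-related reactions, and Section 5.8.8 is about rituximab-induced ones.

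2. *Treatment-related Grade 3 arrhythmia.* It is a cardiac event of Grade 3, so Section 5.9.2.1 stops both drugs. It is also in Table 6, which names rituximab. Relatedness could explain why an unrelated arrhythmia appears only in Table 6, but not this case.

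3. *Debio 1562 in cases 1 and 2.* Section 5.9.2.2 calls for a Debio 1562 dose reduction for other non-hematologic toxicities of Grade 3 or higher, and its exceptions do not include cardiac or skin events. The opening of Section 5.8 leaves reduction or discontinuation to clinical judgment for Grade 3-4 non-hematologic toxicity. Neither text settles the matter.

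4. *Grade 1 rise in creatinine.* It meets the ungraded trigger in Section 5.8.5. It does not meet the Table 6 row.

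5. *Infection.* If *serious* in Section 5.8.7 has the meaning of the SAE definition in Section 9.1.1.2, a Grade 2 infection that needs inpatient admission meets Section 5.8.7 but not Table 6. A Grade 3 infection that meets no seriousness criterion meets Table 6 but not Section 5.8.7. This case depends on that reading of the word.

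Count: skin, arrhythmia and renal give 3 of the 8 Table 6 rows; infection makes it 4 of 8.

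**The case against.** The best defense is that the rules add up rather than conflict. Table 6 and Section 5.8 say that rituximab stops; they never say that Debio 1562 must go on. Stopping both drugs therefore satisfies every sentence literally. The permission in Section 5.9.2.2 is only a permission, given for rituximab intolerance. Likewise, the absence of an event from Table 6 is not an instruction to continue rituximab, so the triggers could be applied as a union. Section 5.8 also says discontinued where Table 6 says permanently discontinued, so the two may not be the same rule.

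Much of this stands as a caution. A reader might infer that Table 6 orders Debio 1562 to be continued. It does not, and the point is limited to the fate of Debio 1562 being unclear. The word *serious* in Section 5.8.7 may also be informal, which is why infection is held less firmly.

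The additive reading is, however, stated nowhere. For treatment-related events it leaves the arrhythmia row, and for rituximab-related skin reactions the mucocutaneous row, with no work to do in a rituximab-only table. A union of triggers does the same to the Grade 3 threshold for renal failure.

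Two further points limit the consequences. The SAP listings show the action taken for each drug, so what was done to a patient will be known; what is uncertain is what the protocol required. And Section 1.9 reports that enrollment was complete by April 2020, so few patients may benefit from a clarification, although extended treatment is possible and the SAP tables still need one list.

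**Conclusion.** The point holds as an inconsistency between stated rules. It is firm for skin reactions and arrhythmias (which drugs stop) and for renal events (what triggers the stop). It is conditional for infections, because it rests on reading *serious* in its SAE sense.

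Its size is 3 of 8 Table 6 rows, or 4 with infection. A reader might want to turn this into a number of patients by applying an assumed incidence to the approximately 75 planned. The documents do not support that: they give no incidence for these events in this trial, and many events, such as an infection that is both serious and Grade 3, would meet both rules and raise no question. A reader might also infer that sites did treat like patients differently. The documents report nothing of the kind; they only leave room for it.

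This should be corrected, since it concerns patient safety and the meaning of two planned safety tables. It does not affect the response analysis plan as written.

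**What to change.** The sponsor's medical team should reconcile Sections 5.8.5 to 5.8.8, 5.9.2.1, 5.9.2.2 and Table 6 so that each event has one trigger and one statement of which drug or drugs stop, and whether permanently. If *serious* in Section 5.8.7 is meant in the SAE sense, the text should say so. Which trigger and which drug is a clinical decision, and this review takes no position on it.

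The dose-modifying-event table in SAP Section 10.3.1 should then be derived from the reconciled list, and the table of discontinuations by study treatment read against it. The cost is clarifying text in the protocol and a reference in the SAP; no new procedure or data collection is needed.

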***Non-hematologic events:***

- Grade 3 nausea, vomiting or diarrhea, lasting more than 48 hours, despite the use of optimal supportive care
- Other non-hematologic toxicities ≥ Grade 3 except for the following:
  - AEs related to underlying disease
  - Isolated, asymptomatic Grade 3 laboratory biochemistry abnormalities that last for ≤ 7 days or have not been optimally managed

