***Other events:***

- Two dose delays (on the first day of two consecutive cycles) due to unmet retreatment criteria

Dose of Debio 1562 can be reduced for only once for a given patient, and it cannot be re-escalated. If a patient cannot tolerate treatment with Debio 1562, both Debio 1562 and rituximab should be discontinued.

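### A treatment-related Grade 4 non-haematologic event is on both the stop list (5.9.2.1) and the reduce list (5.9.2.2), and no sentence says which governs

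*Protocol*

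**What the plan says.** **Stop list.** Protocol 5.9.2.1 opens: "Both Debio 1562 and rituximab should be permanently discontinued in the case of the following treatment-related events". Its entries include "Other non-hematologic events of Grade 4 severity", cardiac events and neuropathy of Grade 3 or higher, and, with a ≥ sign in front, "Grade 3 cutaneous reactions related to rituximab treatment".

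**Reduce list.** Protocol 5.9.2.2 says "Dose of Debio 1562 should be reduced in patients experiencing the AEs below". Under non-haematologic events it lists "Other non-hematologic toxicities ≥ Grade 3 except for the following". The two exceptions are events due to the underlying disease, and certain isolated, symptom-free Grade 3 biochemistry findings.

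**General guidance.** Protocol 5.8 says "Investigators should reduce or discontinue Debio 1562 for Grade 3-4 non-hematologic toxicities based on clinical judgment, and should manage rituximab induced toxicity per label", with a pointer to 5.9. Under 5.9.1, dosing waits until non-haematologic toxicity (alopecia aside) is Grade 2 or lower or back to baseline. After more than 21 "days due to unmet retreatment criteria, both study treatments should be discontinued". If recovery comes sooner, treatment resumes at the planned or a lower dose, with a reference back to 5.9.2.

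**Thrombocytopenia.** Grade 4 lasting more than 7 days stops treatment (5.8.2 and 5.9.2.1). A second Grade 4 episode lasting less than 7 days leads to a reduction (5.9.2.2).

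**Switch.** The synopsis and 5.7.4.1 let a QW patient move to Q3W during the pandemic and give 0.7 mg/kg as the dose. Neither mentions a patient who has already been reduced. 5.9.2.2 says "Dose of Debio 1562 can be reduced for only once for a given patient, and it cannot be re-escalated".

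**The concern.** The two lists prescribe different actions for the same event, and no sentence ranks them. A site that works from the reduce bullet, or relies on the clinical judgment allowed in 5.8, could restart Debio 1562 at a lower dose after a related toxicity that 5.9.2.1 says ends treatment. The recovery rule in 5.9.1 narrows this to patients who recover within 21 days, but then sends the site back to 5.9.2, where both lists apply.

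The switch text raises a smaller question of the same kind. A site reading it without 5.9.2.2 could give a reduced patient 0.7 mg/kg. Protocol 1.6 says that peak concentration may be associated with neutropenia, so the size of the single infusion matters as well as the cycle total.

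What is at stake is patient safety at the margin. No efficacy estimate or test depends on it.

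**Working it through.** **1. The overlap.** Take a treatment-related, non-haematologic Grade 4 event that is not due to the lymphoma.

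- 5.9.2.1: related and Grade 4, so both drugs stop.
- 5.9.2.2: non-haematologic and at least Grade 3, so Debio 1562 is reduced. The bullet has no upper grade limit.
- Exceptions: the event is not due to underlying disease, and the laboratory exception covers Grade 3 only. Neither applies.

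Both instructions are met. The same steps give the same result for a related cardiac event, neuropathy or rituximab-related cutaneous reaction of Grade 3 or higher; the laboratory exception concerns biochemistry findings and does not cover them.

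**2. The 7-day boundary.** The stop applies at more than 7 days and the reduction, at a second occurrence, at less than 7. A second episode of exactly 7 days triggers neither, although a shorter second episode does trigger a reduction.

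**3. The switch dose.** Inputs: QW doses 0.4, 0.2 and 0.2 mg/kg; cohort B reductions 0.4 → 0.2 and 0.2 → 0.1; cohort A reduction 0.7 → 0.4 (5.9.2.2). The unreduced total is 0.4 + 0.2 + 0.2 = 0.8 mg/kg per cycle, which reproduces the figure in 1.6. The protocol does not say whether a reduction lowers all three weekly doses, so the possible cases are shown. Ratio = new dose / old dose.

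| QW state before switch | Cycle total | Largest infusion | Total, to 0.7 | Largest, to 0.7 | Total, to 0.4 | Largest, to 0.4 |
|---|---|---|---|---|---|---|
| All three reduced | 0.2 + 0.1 + 0.1 = 0.4 | 0.2 | 0.7/0.4 = 1.75 | 0.7/0.2 = 3.50 | 0.4/0.4 = 1.00 | 0.4/0.2 = 2.00 |
| Day 1 only reduced | 0.2 + 0.2 + 0.2 = 0.6 | 0.2 | 0.7/0.6 = 1.17 | 3.50 | 0.4/0.6 = 0.67 | 2.00 |
| Days 8 and 15 only reduced | 0.4 + 0.1 + 0.1 = 0.6 | 0.4 | 1.17 | 0.7/0.4 = 1.75 | 0.67 | 0.4/0.4 = 1.00 |

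For an unreduced patient the cycle total falls: 0.7/0.8 = 0.875. For a reduced patient, 0.7 mg/kg would raise the total 1.17 to 1.75 times and the largest infusion 1.75 to 3.50 times. The cohort A reduced level of 0.4 mg/kg never raises the total, but it doubles the largest infusion if Day 1 had been reduced.

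**4. Who is exposed, and when.** Protocol 1.9 gives three patients on QW on 14 April 2020, all permitted to switch, with enrolment complete. Assume that the last first dose was no later than Amendment 6 (24 April 2020, SAP 1). Six cycles take 6 × 21 = 126 days, to 28 August 2020. A 21-day delay at each of the five later cycles adds 5 × 21 = 105 days, to 11 December 2020. SAP 3.1 is dated 7 May 2021, 147 days after that.

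**The case against.** The case for leaving the text alone has weight. The heading of 5.9.2.1 speaks of permanent discontinuation, and once both drugs are stopped no dose is left to reduce. The scopes also differ: 5.9.2.1 names related events, while the reduce bullet is a catch-all that keeps a role for Grade 3 events and for Grade 4 events not related to treatment. Table 4 permanently discontinues treatment for a Grade 4 infusion reaction, and 5.8.2 repeats the stop for prolonged Grade 4 thrombocytopenia; both fit a stop-first approach. Section 5.8 can be read as introducing two lists, one for each action. All of this supports stopping as the natural reading. It does not supply the missing sentence, and the reference in 5.8 to clinical judgment makes a mandatory stop look optional.

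On the switch, a reader might infer that the text would re-escalate a reduced patient. The documents do not support that. 5.9.2.2 bars re-escalation for any patient, the switch is optional and decided by the treating physician, switched patients follow the cohort A schedule, and no document says that any of the three QW patients had been reduced. The 3.50-fold figure needs both a Day 1 reduction and a site that overlooks 5.9.2.2. What stands is a missing cross-reference and no named Q3W dose for a reduced patient.

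The timing objection also stands: scheduled dosing had probably ended before the current SAP.

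**Conclusion.** The overlap between 5.9.2.1 and 5.9.2.2 is in the text and should be corrected. It reaches only patients with a related Grade 4 non-haematologic event, or a related cardiac event, neuropathy or rituximab-related cutaneous reaction of Grade 3 or higher, who recover within the 21-day limit. The documents give no frequency for these events. The 7-day gap and the switch wording are minor: the first needs a second episode of exactly 7 days, and the second concerns at most three patients.

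A reader might go further and infer that the protocol permits continued treatment after any listed stop event, or that the efficacy results are in doubt. Neither follows. The stop rule is explicit and is the natural reading. The definition of objective response, the sample size and the error rates do not depend on these rules.

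The dose range rests on the assumption that a reduction may lower some or all of the weekly doses. The timing rests on the assumption that no first dose came after 24 April 2020; on that basis an amendment would reach only patients exceptionally extended beyond six cycles.

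**What to change.** 1. In 5.9.2.2, limit the non-haematologic bullet to events not listed in 5.9.2.1. Alternatively, state that 5.9.2.1 takes precedence over 5.9.2.2 and 5.8.
2. In 5.9.2.2, change the thrombocytopenia duration from < 7 to ≤ 7 days. Leave the stop rule as it is.
3. In the synopsis and 5.7.4.1, state that a previously reduced QW patient may not switch to 0.7 mg/kg. The sponsor should either keep the patient on reduced QW or name a reduced Q3W dose. The cohort A level of 0.4 mg/kg is a candidate on the cycle total, but the sponsor would have to justify doubling the largest infusion if Day 1 had been reduced.

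The cost is two sentences and one symbol in a clarification letter or amendment.

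If dosing has ended, use the planned listings instead: dose-modifying events with relationship and action taken (SAP 10.3.1), QW-to-Q3W switches (SAP 10.1.2) and by-subject infusions (SAP 10.4). Report any patient who continued Debio 1562 after a 5.9.2.1 event, and any who switched after a reduction. That is a short note in the study report and needs no new analysis.
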